8.4 Safety Analyses

Safety analyses will be performed using the Safety Population, unless otherwise specified.

Safety measurements will include AEs, clinical laboratory tests (i.e. serum chemistry, hematology and urinalysis), ECGs, physical exams and vital signs. All safety data will be summarized by treatment.

Baseline values for clinical laboratory tests, vital signs and ECGs will be defined as the last evaluation performed prior to administration of study drug.

8.4.1 Adverse Events

All AEs will be coded to system organ class (SOC), and preferred term (PT), using the latest Medical Dictionary for Regulatory Activities coding dictionary (version to be specified in the clinical study report). All reported AEs will be listed, but only TEAEs will be summarized.

The incidence of all TEAEs will be summarized by treatment. In the summary tables, subjects may be counted under multiple SOCs and PTs, but for each SOC and PT, subjects are only counted once. If a subject has the same AE on multiple occasions, the highest severity (severe > moderate > mild) or drug relationship (definite > probable > possible > not likely related > unrelated) recorded for the event will be presented. If severity is missing, subjects will be included as missing (for severity). If drug relationship is missing, subjects will be included in related tables (e.g., considered related). Summary tables will be organized by SOC, then PT.

The following summaries will be presented for TEAEs:

- Overall Summary of TEAEs by Treatment
- Incidence of TEAEs by Treatment, System Organ Class, and Preferred Term
- Incidence of Treatment Emergent Serious Adverse Events by Treatment, System Organ Class, and Preferred Term

Subjects who prematurely discontinued due to TEAEs and subjects with serious TEAEs will be listed.

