Clinical Laboratory Changes: It is the investigator's responsibility to review the results of all laboratory tests as they become available. For each abnormal laboratory test result, the investigator needs to ascertain if this is a clinically significant change from baseline for that individual subject. This determination, however, does not necessarily need to be made the first time an abnormal value is observed. The investigator may repeat the laboratory test or request additional tests to verify the results of the original laboratory tests. If this laboratory value is determined to be a clinically significant change from baseline for that subject, this is considered an AE.

Hypoglycemia will be defined as any fasting plasma glucose (FPG) value < 70 mg/dL and documented as described in [Section 6.7.4.4](#).

Any increase in liver function tests (aspartate aminotransferase (AST), alanine aminotransferase (ALT), or bilirubin) greater than 3 times the upper limit of normal (ULN) for the laboratory utilized will be considered a clinical laboratory adverse event.

An increase in creatinine from baseline by 0.5 mg/dL or more will be reported as a laboratory adverse event.

Severity: Adverse events will be graded on a 3-point scale and reported as indicated on the CRF. The intensity of an adverse experience is defined as follows:

1 = Mild: discomfort noticed, but no disruption to daily activity

2 = Moderate: discomfort sufficient to reduce or affect normal daily activity

3 = Severe: inability to work or perform normal daily activity

Investigational Product Causality: The site and database should ask for the causality relative to the study compound. Relationship of an adverse event to dosing will be assessed as follows:

Definite: There is a reasonable causal relationship between the investigational product and the AE when the event responds to withdrawal of the investigational product (dechallenge), and recurs with administration of the investigational product (rechallenge).

Probable: There is a reasonable causal relationship between the investigational product and the AE. The event responds to dechallenge. Rechallenge is not required.

Possible: There is a reasonable causal relationship between the investigational product and the AE. Dechallenge is lacking or unclear.

Not Likely: There is a temporal relationship to investigational product administration, but there is not a reasonable causal relationship between the investigational product and the event.

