- Draw blood for hematology, serum chemistry, electrolytes and lipids pre-dose
- Conduct urinalysis on clean-catch urine pre-dose
- Perform abbreviated physical examination pre-dose
- Collect vital signs collected including pulse, temperature, respiratory rate, and blood pressure taken in the sitting position after at least 5 min of rest, pre-dose and 4 h post-dose
- Conduct 12-lead ECG in the supine position after at least 5 min of rest, pre-dose, 4 and 8 h post-dose
- Administer both bexagliflozin and digoxin to subjects as described in [Section 5.3](#)
- Collect plasma samples for PK analysis as detailed in [Section 6.6](#)
- Assess adverse events and record concomitant medications as described in [Section 6.7](#)

DAY 4

- Administer bexagliflozin to subjects as described in [Section 5.3](#)
- Conduct 12-lead ECG in the supine position after at least 5 min of rest, 24 h post-dose digoxin
- Collect plasma samples for PK analysis as detailed in [Section 6.6](#)
- Assess adverse events and record concomitant medications as described in [Section 6.7](#)

DAY 5 TO DAY 7

- Administer bexagliflozin to subjects as described in [Section 5.3](#)
- Collect plasma samples for PK analysis as detailed in [Section 6.6](#)
- Assess adverse events and record concomitant medications as described in [Section 6.7](#)

DAY 8

- Draw blood for hematology, serum chemistry, electrolytes and lipids as detailed in [Section 6.6](#)
- Administer bexagliflozin to subjects as described in [Section 5.3](#)
- Collect plasma samples for PK analysis as detailed in [Section 6.6](#)
- Collect vital signs including pulse, temperature, respiratory rate, and blood pressure in the sitting position after at least 5 min of rest as described in [Section 6.4](#)
- Conduct urinalysis on clean-catch urine
- Assess adverse events and record concomitant medications as described in [Section 6.7](#)
- Discharge subjects after all study activities are completed

For subjects who are terminated from the study for any reason after dosing, all activities for the study termination day except for PK sample collection must be completed. The reason for termination must be entered onto the case report form.

7.2.2 Period 2

DAY 18

- Admit Group 1 subjects to the Phase 1 clinic
- Perform abbreviated physical examination as described in [Section 6.3](#)
- Conduct urine pregnancy test for all female subjects
- Assess adverse events and record concomitant medications as described in [Section 6.7](#)

DAY 19

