9.6.2 Hypoglycemia

Hypoglycemia as defined in [Section 6.7.4.4](#) will be presented in listings and summarized.

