6.3.3.1 Treatment-Emergent AE (TEAE)

An adverse event is considered treatment-emergent if it occurs after digoxin and/or bexagliflozin administration and if the date –time or date of onset is on or after the date of first dose of study medication, or worsens during the treatment period (intensity/severity grades worsen).

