6.3.3.4 Adverse Events Counting Rules

1. A subject with more than one different AE in a particular system organ class (SOC) will be counted only once in the total of subjects experiencing adverse events in that particular SOC.
2. A subject having experienced the same event (AE preferred term) more than once during the study will be counted only once in the number of subjects with that event.
3. A subject having experienced the same event (AE preferred term) more than once during the study with a different severity or seriousness, it will be counted only once with the worst grade and seriousness respectively.
4. A subject having experienced the same event (AE preferred term) more than once during the study with a different causal relationship to the study drug, it will be counted only once by considering the most-related documented degree of relationship.

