8.4.2 Laboratory Data

Summary tables for laboratory parameters (including hematology and chemistry) will be summarized for each treatment. Summaries for change from baseline for hematology, and chemistry parameters will include descriptive statistics (the number of non-missing values, mean, standard deviation, median, minimum and maximum) for values and change from baseline values for all continuous variables, and frequency counts and percentages for categorical variables, by treatment. Subjects with laboratory data outside the normal range will be listed with abnormal values flagged.

Urinalysis results will be listed.

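### Bexagliflozin-only lead-in findings count under Treatment A, so laboratory-threshold events lean towards A by a factor of about 1.2 to 2.0 with no drug effect

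*SAP*

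**What the plan says.** The secondary objective (Protocol 2.2, SAP 2.2) is the safety and tolerability of digoxin given with bexagliflozin. The planned tabulation is in SAP 8.4.1: "The incidence of all TEAEs will be summarized by treatment". SAP 6.3.3.1 sets the starting point: "An adverse event is considered treatment-emergent if it occurs after digoxin and/or bexagliflozin administration". SAP 6.3.3 assigns an event to Period 1 until just before the first dose of Period 2. SAP 6.3.3.4 says that a subject with repeated occurrences of one preferred term "will be counted only once in the number of subjects with that event".

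Protocol 6.7 defines some events by a laboratory value alone. For glucose: "Hypoglycemia will be defined as any fasting plasma glucose (FPG) value < 70 mg/dL". For creatinine: "An increase in creatinine from baseline by 0.5 mg/dL or more will be reported as a laboratory adverse event". A liver test above 3 times the upper limit of normal is also an adverse event. Protocol 9.6.2 adds that hypoglycaemia "will be presented in listings and summarized"; the SAP text has no matching summary.

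The schedule (Protocol Section 7 and Appendix 1) places one laboratory draw in Treatment A after two days of bexagliflozin and before digoxin. For Day 3 of Group 1, Protocol 7.2.1 reads "Draw blood for hematology, serum chemistry, electrolytes and lipids pre-dose"; Day 17 of Group 2 is the same. Treatment B has no such draw.

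**The concern.** When each subject counts once per term, incidence is the chance of at least one positive look. It rises with the number of looks even if the chance at each look never changes. Treatment A has its own lead-in looks, and the plan restricts the comparison neither to matched time points nor to a per-look denominator. A low glucose found on Day 3 before digoxin would appear in the column that a reader takes to be digoxin plus bexagliflozin, although it says nothing about that combination. In an 18-subject safety table, one or two extra subjects in a row can be read as a signal.

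**Working it through.** **Inputs.** The documents state no look count, event rate or within-subject correlation, so there is no plan figure to reproduce. I counted scheduled looks per subject from Protocol Section 7 and Appendix 1. A footnote to Appendix 1 makes the clinical laboratory draws pre-dose.

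| Looks per subject | Group 1, A | Group 1, B | Group 2, A | Group 2, B | Mean A v B |
|---|---|---|---|---|---|
| Laboratory, first dose to discharge | 2 (Days 3, 8) | 1 (Day 24) | 2 (Days 17, 22) | 1 (Day 6) | 2 v 1 |
| Laboratory, SAP 6.3.3 window | 3 (adds Day 19 pre-dose) | 1 | 2 | 2 (adds Day 15 pre-dose) | 2.5 v 1.5 |
| Laboratory, digoxin to discharge | 1 | 1 | 1 | 1 | 1 v 1 |
| ECG, first dose to discharge | 5 | 4 | 6 | 3 | 5.5 v 3.5 |
| ECG, SAP 6.3.3 window | 6 | 4 | 6 | 4 | 6 v 4 |
| ECG, 4, 8 and 24 h after digoxin | 3 | 3 | 3 | 3 | 3 v 3 |

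With 9 subjects per group, the SAP window gives 9 × (3 + 2) = 45 laboratory looks in A and 9 × (1 + 2) = 27 in B, or 1.67:1.

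**Formula.** Let p be the chance of an event at any look, equal in A and B (no drug effect), and F(k) the chance of at least one event in k looks.

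- Independent looks: F(k) = 1 − (1 − p)^k.
- Within-subject correlation ρ (beta-binomial): F(k) = 1 − ∏ (b + i)/(a + b + i) for i = 0 to k − 1, with a = p(1 − ρ)/ρ and b = (1 − p)(1 − ρ)/ρ.
- First dose to discharge: A/B = F(2)/F(1) = (2 − p) − ρ(1 − p).
- SAP window: A = ½[F(3) + F(2)], B = ½[F(1) + F(2)].

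**One case: p = 5%, independent looks.**

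- First dose to discharge: A = 1 − 0.95² = 0.0975, B = 0.05, ratio 1.95. In 18 subjects, 1.76 v 0.90, an excess of 0.86.
- SAP window: F(3) = 1 − 0.95³ = 0.1426, so A = (0.1426 + 0.0975)/2 = 0.1201 and B = (0.05 + 0.0975)/2 = 0.0738, ratio 1.63. In 18 subjects, 2.16 v 1.33, an excess of 0.83.

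**Range.** Ratio A/B with no drug effect, for p = 1%, 5%, 10%, 20%, 30%:

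| ρ | First dose to discharge | SAP 6.3.3 window |
|---|---|---|
| 0 | 1.99, 1.95, 1.90, 1.80, 1.70 | 1.66, 1.63, 1.59, 1.51, 1.44 |
| 0.3 | 1.69, 1.66, 1.63, 1.56, 1.49 | 1.45, 1.43, 1.41, 1.36, 1.32 |
| 0.5 | 1.50, 1.48, 1.45, 1.40, 1.35 | 1.33, 1.32, 1.30, 1.27, 1.23 |
| 0.8 | 1.20, 1.19, 1.18, 1.16, 1.14 | 1.14, 1.13, 1.13, 1.11, 1.10 |

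For correlations up to 0.5 the range is 1.23 to 1.99. At 0.8 it shrinks to 1.10 to 1.20 but stays above 1.

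**After the fix.** Each subject has one 120 h laboratory look and three ECG looks per treatment, so the ratio expected with no drug effect is 1.0.

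**The case against.** The best defence is that the plan's own rules already soften the problem and that little depends on it. Much of this stands.

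- **Attribution.** Under SAP 6.3.3 the Day 15 pre-dose draw in Group 2 belongs to Treatment B, which makes that group 2 v 2. A reader might infer that the surplus follows treatment in both sequences. That holds from first dose to discharge, but not under the SAP window, where it sits entirely in Group 1.
- **Size.** A reader might infer that threshold events will appear twice as often in A. That needs rare events, independent looks in the same person and no attribution across periods. Twice is the upper end.
- **Which events.** A reader might extend the point to vital signs (4 v 2) and urinalysis (2 v 1 from first dose to discharge). Neither has a numerical adverse event trigger in the documents, and SAP 8.4.2 only lists urinalysis. ECG events need the investigator's judgement of clinical significance (Protocol 6.5), so the formula does not describe them directly. Nor is the ECG surplus two in each group from first dose to discharge: it is 1 in Group 1 and 3 in Group 2, and becomes 2 in each only under the SAP window.
- **Laboratory tables.** SAP 8.4.2 says "Summary tables for laboratory parameters (including hematology and chemistry) will be summarized for each treatment", but plans descriptive statistics for values and changes, with out-of-range values listed. SAP 6.1.1 analyses by nominal visit, so Day 3 can be read apart from Day 8. The problem lies in the event incidence table, not there.
- **Consequence.** SAP 3.3 rules out formal hypothesis testing, and all events are listed, so a careful reader could trace one to a pre-digoxin draw.

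What remains is that the summary table itself does not make this separation, and that in every scenario computed the lean is towards A.

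**Conclusion.** The point holds as a cheap improvement. It is not a threat to the trial's main conclusion, which rests on digoxin pharmacokinetics. For the laboratory-threshold events of Protocol 6.7, the incidence table would show an A/B ratio of about 1.2 to 2.0 with no drug effect. At an assumed 5% per look this is an excess of at most about 0.9 of 18 subjects. The figures assume an equal event chance at every look, correlation from 0 to 0.5, event rates from 1% to 30%, all subjects completing, no unscheduled repeats, and counting once per term within each treatment.

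A reader might take the surplus to be a feature of giving the two drugs together. The documents do not support that: from digoxin to discharge, laboratory looks are 1 v 1 and ECG looks average 3.5 v 3.5. The first-dose-to-discharge surplus comes from the bexagliflozin-only lead-in; the SAP window then moves the Period 2 pre-dose looks to the Period 1 treatment.

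**What to change.** In SAP 8.4.1, and in a SAP counterpart to the Protocol 9.6.2 hypoglycaemia summary:

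1. Base the A-versus-B comparison of measurement-defined adverse events on looks shared at the same time after digoxin: the 120 h laboratory draw (Days 8 and 24 in Group 1, Days 22 and 6 in Group 2) and the 4, 8 and 24 h ECGs.
2. Show events found after the first bexagliflozin dose and before digoxin in a separate lead-in row.
3. Show events found at the Period 2 pre-dose looks (Day 19 or Day 15) and at the discharge ECGs that exist only in Period 2 (Day 24 or Day 22) in a further row for unmatched looks. Without it these events would fall in no row.
4. Give the number of scheduled looks with each row, and keep all events in the listings.

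The hypoglycaemia row also needs one cut-off: Protocol 6.7 uses values below 70 mg/dL, while Protocol 6.7.4.4 includes 70 in its documented categories. The two must be reconciled.

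The cost is SAP wording and two table rows, with no new data. The drawback is that fewer events enter the A-versus-B contrast.

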8.4.2 Laboratory Data

Summary tables for laboratory parameters (including hematology and chemistry) will be summarized for each treatment. Summaries for change from baseline for hematology, and chemistry parameters will include descriptive statistics (the number of non-missing values, mean, standard deviation, median, minimum and maximum) for values and change from baseline values for all continuous variables, and frequency counts and percentages for categorical variables, by treatment. Subjects with laboratory data outside the normal range will be listed with abnormal values flagged.

Urinalysis results will be listed.

8.4.3 Vital Signs

Summary tables for vital signs data will include descriptive statistics (the number of non-missing values, mean, standard deviation, median, minimum and maximum) for values and change from baseline values by treatment.

A listing of vital signs results will be provided for all subjects in the Safety Population.

8.4.4 Electrocardiogram (ECG)

ECG parameters (RR interval, PR interval, QRS duration, QT interval, and QTcB interval) will be summarized by changes from baseline values by treatment and treatment group using descriptive statistics. For each parameter, only subjects who had both baseline and a post-baseline assessment will be included in the summary.

A listing of ECG results will be provided for all subjects in the Safety Population.

8.4.5 Physical examinations

Physical examination results will be presented in individual subject data listings.

8.4.6 Pregnancy Test

Pregnancy test results prior to treatment will be listed.

9. ANALYSES PERFORMED BEFORE DATABASE CLOSURE

No interim analyses are planned for this study.

10. CHANGES FROM METHODS PLANNED IN THE PROTOCOL

Any changes to methods planned in this SAP will be documented in a revision to this statistical plan prior to database lock, or identified in the clinical study report.

11. STATISTICAL SOFTWARE

The statistical software to be used for generation of the tables, listings, and figures is SAS[®] version 9.4.

13. APPENDIX 1 DATA HANDLING RULES

Category	Description	Data Handling Rules
Demographics	Age at informed consent	
$Age = integer ([date\ of\ informed\ consent\ signed - date\ of\ birth + 1]/365.25)$
 
If in date of birth, only day is missing, it is imputed by 15th of the month of birth; both day and month are missing, it is imputed by July 1st of the year of birth.

Baseline		Baseline was defined as the last assessment made before the dose of the investigational product.
Vital Signs/ECG/Lab (Hematology, Chemistry)	Change from baseline	$Change_t = Value_t - Value_{Baseline}$

14. APPENDIX 2 SAS CODE FOR STATISTICAL ANALYSES

This section will be completed after examining the existing data and prior to the final signoff of this SAP.

Test	Table/Figure	SAS Codes for Modeling
ANOVA using a linear mixed-effects model.	PK endpoints requiring ANOVA.	
Analysis using PROC MIXED in SAS with SEQ, SUBJ, PERIOD, and TRTP identifying SEQUENCE, SUBJECT, PERIOD and TREATMENT variables. “Y” denotes the response measure (log (AUC), log (C_{MAX})). “KR” denotes Kenward-Roger method. “CL” denotes confidence limits.
 <pre> PROC MIXED METHOD=REML; CLASS SUBJ SEQ PERIOD TRTP; MODEL Y = SEQ PERIOD TRTP/ DDFM=KR; RANDOM SUBJ(SEQ); LSMEANS TRTP/ PDIF CL ALPHA = 0.10; ESTIMATE 'T/R' TREAT -1 1/CL ALPHA = 0.1; RUN; </pre> 
Anti-log transformation to obtain the geometric means. “GEO” denotes geometric and “LS” denotes least square.
 <pre> DATA LSMEANS; SET LSMEAN GEOLSMEAN = EXP(ESTIMATE); RUN; </pre> 
Anti-log transformation to obtain the ratio of geometric means (point estimate) and 90% confidence interval (CI) – lower and upper bounds.
 <pre> DATA DIFFS; SET ESTIMATE; RATIO = EXP(ESTIMATE)*100; LOWER = EXP(LOWER)*100; UPPER = EXP(UPPER) * 100; RUN; </pre>

**15. APPENDIX 3 REFERENCE RANGES AND CLINICALLY RELEVANT CHANGES
FROM BASELINE FOR MARKED LABORATORY ABNORMALITIES**

<To be inserted>

16. APPENDIX 4 MOCKUP TABLES, LISTINGS, AND GRAPHS (TLGs)

Mockup tables, listings, and graphs are presented in a separate document.
